# Estimation of the influence function of the IPS-weighted Breslow estimator: $\varphi_n^{\Lambda}$

The influence function  $\varphi_0^{\Lambda}$  can be consistently estimated using the following:

$$\varphi_n^{\Lambda}(o_i) \equiv \frac{r_i \delta_i I\{y_i \le t\}}{\pi_i^* S_n(y_i)} + \nu_n^*(o_i, t, \beta_n) - \frac{1}{n} \sum_{\{j:\delta_j=1\}} I\{y_j \le t\} \left(\frac{r_i I\{y_i \ge y_j\} e^{z_i'\beta_n} + \pi_i^* \nu_n(o_i, y_j, \beta_n)}{\pi_i^* \left(S_n(y_j)\right)^2}\right) - \mu_n(t) \tilde{\ell}_n^*(o_i).$$

This involves the following nuisance estimators:

$$\nu_n^*(o_i, t, \beta_n) \equiv \left(\frac{p_n^1(c_i) - p_n(c_i)r_i}{(p_n^1(c_i))^2}\right) \left(\frac{1}{n} \sum_{\{k:c_k = c_i, r_k = \delta_k = 1\}} \frac{I\{y_k \le t\}}{S_n(y_k)}\right)$$
$$\nu_n(o_i, y_j, \beta_n) \equiv \left(\frac{p_n^1(c_i) - p_n(c_i)r_i}{(p_n^1(c_i))^2}\right) \left(\frac{1}{n} \sum_{\{k:c_k = c_i, r_k = 1\}} I\{y_k \ge y_j\} e^{z'_k \beta_n}\right)$$
$$\mu_n(t) \equiv \frac{1}{n} \sum_{\{j:\delta_j = 1\}} \frac{I\{y_j \le t\} S_n^{(1)}(y_j)}{\left(S_n^{(0)}(y_j)\right)^2}.$$

Estimation of the influence function of conditional survival  $S_n(t|z)$ :  $\omega_0^t$ 

The influence function  $\omega_0^t$  can be consistently estimated using the following:

$$\omega_{n}^{t}(o_{i},z) \equiv e^{z'\beta_{n}} \left( \frac{\delta_{i}I\{y_{i} \leq t\}}{S_{n}^{(0)}(y_{i})} - \frac{1}{n} \sum_{\{j:\delta_{j}=1\}} \frac{e^{z_{i}'\beta_{n}I\{y_{j} \leq t \wedge y_{i}\}}}{\pi_{j}^{*} \left(S_{n}^{(0)}(y_{j})\right)^{2}} + \left( \frac{1}{n} \sum_{\{j:\delta_{j}=1\}} \frac{I\{y_{j} \leq t\}(z-m_{n}(y_{j}))}{\pi_{j}^{*}S_{n}^{(0)}(y_{j})} \right)' \tilde{\ell}_{n}(z_{i},\delta_{i},y_{i}) \right).$$

$$(17)$$

# Estimation of the influence function of the target parameter $\bar{S}_n(t|a)$ : $\varphi_0^{t,a}$

Finally, the influence function  $\varphi_0^{t,a}$  can be consistently estimated using the following:

$$\varphi_n^{t,a}(o_i) \equiv S_n(t|w_i, a) + \frac{1}{n} \sum_{j=1}^n \left( \omega_n^t(o_i, (w_j, a)) - S_n(t|w_j, a) \right).$$
(18)

#### 12.3.5 Univariable CoR: Marginalized Cox modeling for an outcome subject to competing risks (e.g. asymptomatic infection)

If the outcome under study is subject to competing risks, then the Cox model is fit in the same way, except counting the competing risk as right-censoring. Now the parameter being estimated is the marginal conditional cumulative incidence function  $risk_1(t, 1|s) = E_X[P(T \le t, J = 1|s, X, A = 1)]$  where J = 1 is the outcome of interest. To estimate this parameter, we use the fact that the cause *j*-specific hazard  $\lambda_{j1}(t|s, x)$  is linked to the conditional cumulative incidence  $F_{j1}(t|s, x) = P(T \le t, J = j|s, x, A = 1)$  via the formula

$$F_{j1}(t|s,x) = \int_0^t \lambda_{j1}(u|s,x) S_1(u|s,x)$$

where  $S_1$  is the all-cause/overall conditional survival function for the first event of asymptomatic infection or COVID-19, whichever occurs first (i.e., the COV-INF endpoint). Therefore, after fitting the cause J = 1 Cox model, for any fixed t the above formula provides fitted values  $\hat{F}_{j1}(t|s, X_i)$  for each participant i, and then the G-computation estimator of  $risk_1(t, 1|s)$  is

$$\widehat{risk}_1(t,1|s) = \frac{1}{n} \sum_{i=1}^n \hat{F}_{j1}(t|s,X_i).$$

As for the analyses without competing risks, the bootstrap is used for calculating 95% confidence intervals and for testing  $H_0: risk_1(t_F, 1|s) = risk_1(t_F, 1)$ for all s.

#### 12.3.6 Univariate CoR: Nonparametric threshold regression modeling

The van der Laan et al. (2021) extension of the nonparametric CoR threshold estimation method of Donovan et al. (2019) is applied to each of the five nonbaseline subtracted Day 57 antibody markers, using the version that defines the binary outcome Y of interest as Y = 1 if a COVID endpoint occurred during the blinded period of follow-up and Y = 0 otherwise. The analyses adjust for the same baseline factors X as used in the Cox model CoR analyses.

The extension adjusts for baseline covariates by estimating the conditional mean function  $E[Y|S \ge s, X, A = 1]$  using discrete-SuperLearner and then

empirically averaging over the baseline covariates X to estimate the marginal risk  $risk_1^Y(S \ge s) = E_X[P(Y = 1 | S \ge s, X, A = 1)]$  for each threshold s of the the antibody marker in a specified discrete set. We do not perform pooled regression across the thresholds s, which ensures we are totally nonparametric in estimating the threshold dependence of  $risk_1^Y(S \ge s)$  on s. The Super-Learner library includes a range of increasingly flexible parametric learners including logistic regression (glm), bayesian logistic regression (bayesglm), and L1-penalized logistic regression (glmnet). (Two of each learner is included in the library, one with only main-term variables and another with main-term and interaction variables.) An advantage of the nonparametric CoR threshold method compared to Cox modeling that specifies a log linear hazard ratio with the marker is that it can potentially detect a threshold of very low risk. The method is implemented with and without the monotonicity constraint that  $risk_1^Y(S \ge s)$  is monotone non-increasing in s, where the results assuming monotonicity are reported unless there is evidence for violation of this assumption.

The results are reported in the same way that Donovan et al. (2019) reports results in its Figure 2, where point estimates, pointwise 95% confidence bands, and simultaneous 95% confidence bands for  $risk_1^Y(S \ge s)$  are plotted for a range of threshold values. The simultaneous confidence bands cover the entire curve in s with at least 95% probability and are useful for judging whether risk varies over threshold subgroups, whereas the pointwise 95%confidence bands are useful for quantifying precision at particular threshold values. The method uses the same empirical two-phase sampling estimated weights (IPS weights) as used for the other univariable IPWCC CoR analyses. In addition, for each pre-specified risk threshold c set to take values over a grid with lowest value 0, the method is applied to estimate the inverse function  $s_c = inf\{s : E_X[P(Y = 1 | S \ge s, A = 1, X] \le c\}$ , where  $s_c$  is estimated by substitution of the marginal risk function estimate. Note that the substitution estimator of  $s_c$  requires that the marginal risk function is estimated for all thresholds, which is computationally infeasible. Instead, we estimate the marginal risk function on a sufficiently large discrete set and linearly interpolate to obtain marginal risk estimates for all thresholds outside
the discrete set. In order for this estimand to be well defined, we operate (for this estimand only) under the assumption that  $s \mapsto risk_1^Y(S \ge s)$  is monotone. For the substitution-based estimator of the inverse function  $s_c$  to be well-defined, we require the estimate of  $s \mapsto risk_1^Y(S \ge s)$  to be monotone as well. If there is evidence that the function estimate is not monotone then we replace the estimate with its monotone projection, which preserves its theoretical properties (Westling, van der Laan, Carone, 2020).

A plot of point and pointwise 95% confidence interval estimates of  $s_c$  (over the grid of c values) is provided to help indicate marker thresholds defining subgroups with very low risk of outcome. The confidence interval estimates for  $s_c$  are derived directly from the confidence interval estimates for the marginal risk function  $s \mapsto risk_1^Y (S \ge s)$ , and therefore its estimates are compatible with those of the marginal risk function. In addition, a plot of point and simultaneous 95% confidence interval estimates of  $s_c$  (over the grid of c values) is provided, where the simultaneous confidence interval estimates for  $s_c$ are derived directly from the simultaneous 95% confidence band estimates for the marginal risk function  $s \mapsto risk_1^Y (S \ge s)$ , and therefore its estimates are compatible with those of the marginal risk function. In particular, no multiple testing adjustments are needed.

The analysis is done using targeted maximum likelihood estimation (TMLE) as described in van der Laan, Zhang, and Gilbert (2020), and the pointwise and simultaneous simultaneous confidence bands are of the Wald-type, obtained from the asymptotic distribution of the TMLE.

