#### Issue 4: Binary endpoint vs. failure time endpoint

In general, in phase 3 trials with prospective follow-up for event occurrence where right-censoring occurs (either due to administrative censoring or loss to follow-up), it can be advantageous to conduct data analysis in a survival analysis paradigm. Many of the correlates analyses are specified as such. However, because the endpoints are rare, and the rate of loss to follow-up is anticipated to be very low, reliable and interpretable answers may be obtained based on simpler methods that use binary endpoints, and deal with loss to follow-up in a cruder way. If retention is very high, such that bias and precision may be minimally impacted by use of a binary endpoint, some of the correlates analyses may use a binary endpoint. In settings with competing risks, such analyses would treat the endpoint as multinomial and utilize methodology accordingly.

In sum, correlates methods are needed that consider time-to-event or binary endpoints, with or without accounting for a competing risk. In addition, the methods need to be able to handle continuous, discrete, and mixed continuous/discrete failure times.

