#### 12.3.3 Univariable CoR: Marginalized Cox modeling

Time-to-event methods use the Day 57 visit date as the time origin.

The IPWCC Cox regression model designed for case-cohort sampling designs will be used for estimation and inference on hazard ratios of outcomes by Day 57 marker levels, and for estimation and inference on marginalized markerconditional cumulative incidence over time. The models will be fit using the *survey* R package available on CRAN, and will adjust for the baseline factors. We use a method from the survey package that assumes without replacement two-phase sampling and not Bernoulli sampling, which matches the sampling design and approach to weight estimation (Lumley, 2010).

For models with a single antibody marker, a two-phase Cox model with improved efficiency through calibrated weights (Breslow et al., 2009b,a) will be used if there are baseline covariates that predict the antibody marker with  $R^2 > 0.4$ . Based on the phase-two sample, a superlearner model will be fit (using the library specified in Table 7) to predict the antibody marker from the set of collected baseline covariates. The criterion  $R^2 > 0.4$  will be checked based on the association of the fitted values from superlearner and the marker, where the association uses held-out marker values.

Based on the Cox model fit to all available data during blinded follow-up (the period during which participants are blinded to randomization arm assignment), a final time point  $t_F$  near the time of the last observed outcome will be defined. Let T be the failure time, S a Day 57 marker of interest, and X the vector of baseline factors that are adjusted for. With  $S_1(t|s,x) = P(T > t|S = s, X = x, A = 1)$ , the Cox model fit yields an estimate of  $S_1(t|s, X_i)$  for each individual i in the phase-two sample. The marginalized conditional risk  $risk_1(t|s) = E_X[P(T \le t|s, X, A = 1)]$  through time t (for all times t through  $t_F$  simultaneously) is estimated based on the equation

$$risk_1(t|s) = \int (1 - S_1(t|s, x)) dH(x)$$
 (1)

where  $H(\cdot)$  is the distribution of X in A = 1 individuals.

The function  $risk_1(t|s)$  can be estimated by

$$\widehat{risk}_1(t|s) = \frac{1}{n} \sum_{i=1}^n (1 - \hat{S}_1(t|s, X_i)),$$
(2)

where n is the number of vaccine arm participants with phase-one data ( $X_i$  measured). The bootstrap is used to obtain 95% pointwise confidence intervals for  $risk_1(t_F|s)$ .

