This parameter is useful because typically subgroups of interest are defined by having marker response above a threshold. We will plot  $\widehat{risk}_1(t_F|S \ge s)$  vs. swith 95% CIs for continuous S with s varying over the range of S in which the number of cases to estimate  $\hat{S}_1(t|S \ge s, X_i)$  is 5 or more. This type of analysis is also included because it analyzes the same parameter as the nonparametric threshold estimation method described below, providing a way to address the threshold question both by Cox modeling and by nonparametric analysis.

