# 16 Summary of the Set of CoR and CoP Analyses and Their Requirements and Contingencies, and Synthesis of the Results, Including Reconciling Any Possible Contradictions in Results

Table 10 summarizes all of the Stage 1 / Day 57 marker correlates analyses that are done, including contingencies for whether and when each analysis is done. The quantitative version of each marker S, and the tertiles version of each marker S, is common across all of the analyses. All of the Day 57 markers are the versions that are not baseline subtracted, given that the cohort for analysis is baseline negative. Most of the analyses focus on univariate Day 57 markers. The primary reason to do this is the goal to identify a parsimonious correlate based on a single marker without needing to run the

set of assays, and secondary reasons are: (1) the assay readouts are expected to be highly correlated, especially for the ID50 and cID80 readouts from the same pseudovirus neutralization assay, and (2) there is ample precedent for univariate markers being accepted as immunological surrogate endpoints for approved vaccines (Plotkin, 2010).

	Structure	Requirements/Contingencies	
	of	Min No. Vaccine	
Analysis	Day 57 Marker(s)	Endpoints	$\mathbf{Other}$
CoR Cox Model	Tertiles of $S^1$	25	None
	Quant. $S = s^2$	25	None
	Quant. $S \ge s^1$	25	None
CoR Nonpar. threshold	Quant. $S \ge s^1$	35	None
CoR GAM	Quant. $S = s^2$	35	None
CoR threshold log. regr.	Quant. $S = s^2$	25	None
CoR Superlearner 	Quant. $S = s$ , 2FR, 4FR	35	None
CoP: Correlates of VE	Binary $S$	50	None
	Quant. $S = s$	50	BIP with $R^2 \ge 0.25$
CoP: Controlled VE	Quant. $S = s$	50	Feasibility of positivity 
	Tertiles of $S = s$	50	Feasibility of positivity 
CoP: Stoch. Interv. VE	Quant. $S = s$	50	Feasibility of positivity 
CoP: Mediators of VE	Quant. $S = s$	50	Feasibility of positivity 
	Tertiles of $S$	50	Feasibility of positivity 

These analyses are harmonized in addressing the same scientific question of how does endpoint risk vary over vaccinated subgroups defined by S above a threshold.

These exploratory supportive analyses are harmonized in addressing the same scientific question of how does endpoint risk vary over vaccinated subgroups defined by S equal to a given marker value.

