Only this Superlearner analysis uses data from multiple assays and multiple readouts as input features; the other analyses consider one Day 57 biomarker at a time. The positivity

assumptions are as follows. Controlled VE: P(S = s | A = 1, X) > 0 almost surely. Stochastic Interventional VE:  $s_i \in S \implies s_i + \delta \in S | A = 1, X = x$  for all  $x \in \mathcal{X}$  and i = 1, ..., n. Mediators of VE: P(S = s | A = 1, X) > 0 almost surely and

P(S = s | A = 0, X = x) > implies P(S = s | A = 1, X = x) > 0. The quantitative analysis will require that the largest value S observed in the placebo is larger than the smallest value of S observed in the vaccine recipients. This assumption would naturally be satisified for the tertiles analysis. For quantitative S, the assumption is weaker for the Stochastic Interventional VE analysis, such that it is possible that only this analysis of the three will be done.
Some of the analyses include parametric assumptions for characterizing associations (Cox model and threshold analyses, Cox model versions of Controlled VE analyses) and others are nonparametric or approximately so (all other analyses). If parametric and nonparametric analyses of the same type (e.g., Cox model vs. nonparametric CoR analysis of the same association parameter; Controlled VE Cox model vs. nonparametric monotone dose-response) suggest contradictory results, then the interpretation from the nonparametric analysis will be prioritized, given it is more robust and less likely to be an incorrect result. The diagnostic testing of the parametric assumptions will aid this interpretation. As noted above, if the nonparametric analysis suggesting a contradictory result requires a positivity assumption, then its results will only be prioritized if diagnostics support feasibility of the positivity assumption.

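### The nonparametric threshold analysis (SAP 12.3.6) does not estimate the Cox risk at t_F that it is said to match: absolute risk and the threshold s_c come out too low when follow-up is unequal

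*Combined protocol and SAP*

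**What the plan says.** Five places in the SAP bear on this.

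- **Section 12.3.6**: the version chosen there "defines the binary outcome Y of interest as Y = 1 if a COVID endpoint occurred during the blinded period of follow-up"; all other participants are coded zero. It names one set of weights: "The method uses the same empirical two-phase sampling estimated weights (IPS weights) as used for the other univariable IPWCC CoR analyses". The section gives no horizon, censoring weight or time-to-event model. The curve is written risk_1^Y(S ≥ s), and s_c is read off it as the smallest marker value at which risk is at or below c.
- **Section 12.3.3** fits a Cox model with Day 57 as time origin and reports risk by t_F, a final time that "near the time of the last observed outcome will be defined". The Cox curve for S ≥ s "is also included because it analyzes the same parameter as the nonparametric threshold estimation method described below".
- **Section 16, Table 10, footnote 1** is attached to both the Cox S ≥ s row and the nonparametric threshold row: "These analyses are harmonized in addressing the same scientific question".
- **Section 16**, below the table, considers conflicts between parametric and nonparametric analyses of one type. It gives Cox versus nonparametric CoR analysis of a shared association parameter as an example, and "then the interpretation from the nonparametric analysis will be prioritized".
- **Section 7, Issue 4** permits binary endpoints conditionally: "If retention is very high, such that bias and precision may be minimally impacted by use of a binary endpoint". Section 3.2 censors at loss to follow-up or at the last date of available follow-up, and in general admits no follow-up after unblinding.

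**The concern.** A participant who leaves blinded follow-up early without an event is coded exactly like one followed event-free to t_F. The nonparametric curve is therefore the chance of an event within whatever blinded follow-up each participant happened to have, which depends on enrolment date, data cut and date of unblinding. The Cox curve is the chance of an event by one common time. The two agree only if everyone's follow-up reaches t_F.

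Issue 4 does not close the gap. Its argument rests on rare events and low loss to follow-up, and perfect retention does not equalize follow-up under staggered entry, a common data cut and varying unblinding dates.

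At stake are the absolute risk level and s_c, which the SAP plots to point to marker subgroups at very low risk. A reader who lays the two curves side by side would see a difference even under a correct Cox model, and the SAP's own wording would lead them to blame the Cox model.

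**Working it through.** The documents give no risk figure for this analysis, so there is none to reproduce. I used the defaults of the SAP's simulation appendix (24.3.1 and 24.3.4).

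**Inputs.** Baseline-negative placebo risk 0.10 by day 180; VE 0.90; loss to follow-up 0.05 by day 180; administrative follow-up uniform on 4×7 = 28 to 6.5×7 = 45.5 days, applied from Day 57 as in 24.3.4. Events count from day 7 after Day 57. Assumption: t_F equals the longest follow-up, U.

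**Hazards per day.**
- Placebo: −ln(0.90)/180 = 5.853×10⁻⁴
- Vaccine: λ = 5.853×10⁻⁴ × (1 − 0.90) = 5.853×10⁻⁵
- Loss: μ = −ln(0.95)/180 = 2.850×10⁻⁴

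**Formulas.**
- As coded: E[Y] is the average, over c uniform on (L, U), of λ/(λ+μ) × [1 − exp(−(λ+μ)(c − 7))]
- Fixed horizon: R = 1 − exp(−λ(U − 7))

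| Follow-up (days) | E[Y] | R | Ratio |
|---|---|---|---|
| 28–45.5 (SAP default) | 0.00173 | 0.00225 | 0.77 |
| 60–120 (assumed) | 0.00479 | 0.00659 | 0.73 |
| 60–180 (assumed) | 0.00648 | 0.01008 | 0.64 |
| 28–180 (assumed) | 0.00557 | 0.01008 | 0.55 |

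For rare events and no loss, the ratio is close to (mean follow-up − 7)/(U − 7). For the default range that is (36.75 − 7)/(45.5 − 7) = 29.75/38.5 = 0.77.

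**Which censoring matters.** With everyone followed to day 180 apart from 5% loss, E[Y] is 0.00983 against 0.01008, ratio 0.98. Unequal administrative follow-up produces nearly all of the gap.

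**Effect on s_c.** Assume a standard normal marker, hazard ratio 0.5 per SD (β = ln 0.5), follow-up independent of the marker, and c at half the overall t_F risk. For rare events, risk above s relative to overall risk is Φ(β − s)/Φ(−s). Multiply by the ratio k from the table and solve for 0.5:
- k = 1: s = −0.05, the 48th percentile
- k = 0.77: s = −0.65, the 26th percentile
- k = 0.64: s = −1.17, the 12th percentile

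**Relative risk.** With follow-up independent of the marker and a true hazard ratio of 0.50, the risk ratio is 0.500 on both scales for 28–45.5 days and 0.501 on both for 60–180 days. Level and s_c move; shape does not.

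**Shape, if dependence remains.** Illustration: a marker with no effect, correlation −0.3 with follow-up length (Gaussian copula), no adjustment for X, no loss, events counted from day 0.
- Uniform 30–150 days, hazard 10⁻⁴: mean Y is 0.895%, 0.814%, 0.754% and 0.690% for all participants and above the 50th, 80th and 95th percentiles. The decline is 1 − 0.690/0.895 = 23%. The true risk by day 150 is 1 − exp(−0.015) = 1.49% throughout.
- Uniform 28–45.5 days, hazard 5.853×10⁻⁵: 0.215% falls to 0.197%, a decline of 8%.
- Correlation −0.1: declines of 8% and 3% respectively.

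**The case against.** The best defence is that 12.3.6 declares its own parameter, in its own notation, and estimates that parameter consistently. This stands: the fault lies in the claimed equivalence and in carrying the absolute level and s_c over to a fixed horizon, not in bias for the quantity 12.3.6 defines. The section also refers to one version of a cited method, and whether another version adjusts for censoring cannot be checked from the documents.

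A reader might infer more than the documents support:

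- **That a biased analysis overturns the Cox finding.** The Section 16 rule concerns contradictory interpretations, with diagnostics as an aid. A common scale factor neither creates nor reverses a marker-risk association, and 12.4.2 reports CoR p-values only from the Cox regressions, so the significance flags are untouched.
- **That the analysis will show a spurious threshold.** This needs dependence between follow-up and marker that survives adjustment for X. The −0.3 is assumed, and 12.3.6 does adjust for X.
- **That most participants are censored before t_F.** The documents do not give the actual follow-up distribution.
- **That the CoP analyses share the missing horizon.** Sections 14 (multivariate BIP) and 15 already define the outcome by a pre-specified time.

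The very low end of the curve is also robust. If no events are observed above a threshold, estimated risk is essentially zero with or without censoring weights. The distortion in s_c concerns intermediate values of c.

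**Conclusion.** Wrong as written, and worth correcting. The quantity in 12.3.6 is not the Cox risk by t_F, contrary to 12.3.3 and to the harmonization footnote in Table 10, and Section 16 builds a priority rule on analyses sharing a parameter. With unequal blinded follow-up, the absolute curve is too low for t_F risk and s_c is too low: a ratio of 0.77 under the SAP's simulation defaults and 0.55 to 0.73 under the assumed wider ranges. These figures rest on constant hazards, uniform follow-up and t_F at the longest follow-up; an earlier t_F would narrow the gap. The percentile shifts in s_c rest further on the assumed hazard ratio and choice of c. Bias in shape is conditional on residual dependence after X and is not shown to occur.

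**What to change.** In 12.3.6, define Y = I(T ≤ t_F) with the same t_F as the Cox analysis. Handle censoring before t_F by inverse-probability-of-censoring weights or a survival form of the TMLE, with enrolment period and X in the censoring model. Do the same for the dichotomous outcome in 12.4, which also states no horizon.

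If the present outcome is kept:
- delete the same-parameter statement in 12.3.3 and correct footnote 1 of Table 10;
- limit the Section 16 priority rule to analyses that share a horizon and a censoring treatment;
- report s_c together with the follow-up period to which it applies.

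The CoP sections need no change on this point. The cost is SAP wording, one added weight and slightly wider intervals; t_F should be a time at which enough participants remain under follow-up for the weights to be stable.
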